## 7.2 PARTICIPANT DISCONTINUATION/WITHDRAWAL FROM THE STUDY

Participants are free to withdraw from participation in the study at any time upon request.

An investigator may discontinue or withdraw a participant from the study for the following reasons:

- Pregnancy
- Significant study intervention non-compliance
- If any clinical adverse event (AE) necessitating hospitalization
- Disease progression which requires hospitalization
- If the participant meets an exclusion criterion (either newly developed or not previously recognized) that precludes further study participation

The reason for participant discontinuation or withdrawal from the study will be recorded. Subjects who sign the informed consent form and are randomized but do not receive the study intervention may be replaced. Subjects who sign the informed consent form, and are randomized and receive the study intervention, and subsequently withdraw, or are withdrawn or discontinued from the study may also be replaced.

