
### 6.4 STUDY INTERVENTION COMPLIANCE

Compliance of study intervention will be assessed by MUHC emergency department research staff via daily telephone visits. Occurrences of non-compliance will be patient-reported and include number of missed doses for any given day during the on-treatment follow-up period.

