### 7 STUDY INTERVENTION DISCONTINUATION AND PARTICIPANT DISCONTINUATION/WITHDRAWAL

#### 7.1 DISCONTINUATION OF STUDY INTERVENTION

Discontinuation from study supplement or placebo does not mean discontinuation from the study, and remaining study procedures should be completed as indicated by the study protocol. If a clinically significant finding is identified (including, but not limited to changes from baseline) after enrollment, the investigator or qualified designee will determine if any change in participant management is needed. Any new clinically relevant finding will be reported as an adverse event (AE).

Adverse events necessitating discontinuation from the study including removing patients from follow-up telephone visits for any remaining outcome related data collection include any event that would lead to a patient requiring hospitalization. This includes hospitalization related to a suspected adverse event from study drug resulting in unblinding procedures or for worsening respiratory status. Patient self-discontinuation of study intervention due to intolerance affecting future compliance will allow patients to remain in the study to complete any remaining telephone visits for primary and secondary endpoint data collection. Efforts to promote compliance including reinforcing patients to administer study product two hours following a meal will be employed before discontinuing patients from study intervention, but patient refusal to continue with treatment will be considered a dropout with an attempt to collect remaining telephone visits for completeness of endpoint related data capture.

The data to be collected at the time of study intervention discontinuation will include the following:

- Date of study discontinuation
- Reason for discontinuation
- Number of study days completed prior to discontinuation of treatment/study withdrawal
- Total number of patient-reported doses taken of study drug prior to discontinuation of treatment/study withdrawal

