### 9.3 POPULATIONS FOR ANALYSES

All endpoints will be assessed using intention-to-treat analysis. This will include all randomized participants.

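### Section 7.2 lets the investigator withdraw participants from the study for non-compliance, so outcome calls can end for those who skip doses, while 7.1 keeps those who stop the product in follow-up

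*Combined protocol and SAP*

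**What the plan says.** Section 7.2: "An investigator may discontinue or withdraw a participant from the study for the following reasons". The list includes "Significant study intervention non-compliance". It gives no number of missed doses or days, makes no exception for intolerance, and does not say that calls continue. The same section allows participants who were randomised, dosed and then withdrawn to be replaced.

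Section 7.1 states the opposite principle for stopping the product: "Discontinuation from study supplement or placebo does not mean discontinuation from the study, and remaining study procedures should be completed as indicated". Self-discontinuation for intolerance "will allow patients to remain in the study to complete any remaining telephone visits". Of those who refuse further treatment it says "patient refusal to continue with treatment will be considered a dropout with an attempt to collect remaining telephone visits".

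Section 6.3 restricts the seven daily calls to patients who have not been removed from the study. Section 6.4 describes the measurement: "Occurrences of non-compliance will be patient-reported and include number of missed doses for any given day".

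On the analysis population, section 9.3 says "This will include all randomized participants". Section 9.4.2 fills a missing primary outcome by LOCF from the latest total symptom score, and recovery means a score of 0 or 1 out of 36.

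**The concern.** Read together, the sections treat neighbouring cases differently. A participant who stops the capsules because of nausea is kept in follow-up by 7.1. A participant who goes on taking some capsules but skips many because of nausea is not covered by 7.1, and may be withdrawn under 7.2. Through 6.3, that withdrawal ends the calls. With no threshold, the decision is made case by case.

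Missed doses are partly a consequence of the assigned product. Section 2.3.1 cites nausea of 10.2% vs 4.8% for EGCG against placebo, and nausea and stomach distress of 13.5% vs 10.7% for zinc against placebo. Section 2.3.3 expects the nausea risk to be additive. Withdrawals for missed doses may therefore be unequal between arms.

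For an analysis of all randomised participants, ending the calls only replaces scores that could have been collected with a carried-forward one. An early score will usually be unrecovered, so later recoveries would be lost, probably more of them on active.

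**Working it through.** **The plan's own figure.** Section 9.2 assumes 60% vs 30% recovery, two-sided 0.05, 80% power and 1:1 allocation:

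N per arm = {1.96·√(0.45·0.55·2) + 0.84·√(0.3·0.7 + 0.6·0.4)}² / 0.3² = 41.92, rounded up to 42, or 84 in total. The stated figure reproduces. The enrolment target is 50 per arm.

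**Model for the withdrawals.** The documents give no rate of withdrawal for non-compliance, in total or by arm, so every rate below is an assumption. Let w be the proportion withdrawn in an arm and p the true recovery rate. If withdrawal is independent of eventual recovery and each withdrawn participant was last scored unrecovered, then LOCF gives

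observed recovery = p × (1 − w).

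Power is exact for the uncorrected chi-square test with 50 per arm, by enumerating both binomial distributions. The 60% and 30% are the section 9.2 rates, stated there for recovery after five days of treatment and applied here to the analysed endpoint.

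| Withdrawn, active vs placebo | Basis | Observed recovery | Difference (points) | Exact power |
|---|---|---|---|---|
| 0% vs 0% | reference | 60.0% vs 30.0% | 30.0 | 88% |
| 2% vs 1% | low case | 58.8% vs 29.7% | 29.1 | 86% |
| 5.1% vs 2.4% | half the EGCG nausea rates | 56.9% vs 29.3% | 27.7 | 82% |
| 6.8% vs 3.2% | whole planned 5% dropout | 55.9% vs 29.0% | 26.9 | 80% |
| 10.2% vs 4.8% | every nausea case withdrawn (upper case) | 53.9% vs 28.6% | 25.3 | 75% |

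The fourth row splits section 9.2's 5% overall dropout in the ratio 10.2 : 4.8. With equal arms the two rates sum to 10%, so active is 10% × 10.2/15 = 6.8% and placebo is 10% × 4.8/15 = 3.2%.

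**No true effect.** With 45% recovery in both arms and the upper-case rates, the false difference is 0.45 × (1 − 0.102) − 0.45 × (1 − 0.048) = −2.4 points. The standard error of the difference is √(2 × 0.45 × 0.55 / 50) = 9.9 points.

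**Replacement.** Suppose withdrawn participants were replaced and left out. If they would have recovered at rate q, the rate among those analysed is (p − w·q)/(1 − w). Take p = 30% in both arms and the upper-case rates:

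- q = 0: 0.30/0.898 = 33.4% vs 0.30/0.952 = 31.5%, a false difference of +1.9 points for active.
- q = 15%: 0.2847/0.898 = 31.7% vs 0.2928/0.952 = 30.8%, about +0.9 points.

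The sign of the bias therefore depends on how withdrawn participants are handled.

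**The case against.** The strongest reply is that 7.1 already covers the patients who matter most. Those who stop for intolerance stay in follow-up, calls are attempted even after refusal of treatment, and 7.2 is only permissive. This stands as a limit. A reader might infer that calls do end for the participants who tolerate the product worst, but those who stop are the ones 7.1 protects. The gap concerns participants who skip doses without stopping, and for them calls can end, not must end. Nothing in the text says which section prevails for them.

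The second reply concerns size. The 10.2% vs 4.8% is nausea incidence over a 12-month trial, whereas this trial doses for five days. Using it as a withdrawal rate requires every nausea case to become significantly non-compliant and be withdrawn, so it is an upper case. Larger imbalances have no source in the documents. At the plan's own 5% dropout, power stays at about the 80% target, and the upper-case false difference is about a quarter of its standard error (2.4/9.9). That also stands.

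A reader might also infer that adverse events are lost in those who report them. The documents do not support this: 8.3.4 follows all adverse events to resolution, 9.4.4 counts each event once per participant, and 9.4.3 analyses adverse events as a single endpoint. A participant withdrawn after reporting nausea is already counted. What would be missed is new events of other types after withdrawal.

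Finally, intention-to-treat argues against leaving out replaced participants. But 7.2 permits replacement without saying that the replaced participant stays in the analysis, so the direction of bias is not settled by the text.

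**Conclusion.** The point holds as a correctable inconsistency. Section 7.2, read with 6.3, allows outcome collection to end at the investigator's discretion for a reason plausibly related to treatment, and the intention-to-treat analysis gains nothing in return. That non-compliance would be more common on active is an inference from the nausea rates in 2.3.1 and the expectation in 2.3.3; the documents do not state it.

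The effect is modest at plausible rates: exact power of 86% to 80%, against 88% without withdrawals, reaching 75% only in the upper case. These figures rest on 50 per arm, the 60% vs 30% assumption, withdrawal independent of eventual recovery, and an unrecovered last score. Under LOCF the bias most likely runs against active. If withdrawn participants were replaced and omitted, it could favour active.

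**What to change.** 1. Delete "Significant study intervention non-compliance" from the 7.2 reasons for withdrawal from the study.
2. State in 7.1 and 7.2 that missed doses or stopping the product do not by themselves end the daily calls, which run through Day 8 for participants who have not withdrawn consent, and that scores, adverse events and morbidity items collected on those calls are analysed as observed.
3. State that any participant who is replaced remains in the intention-to-treat analysis.
4. Leave the other removal provisions outside this change, including hospitalisation in 7.1 and 7.2 and pregnancy in 8.3.9. A blanket statement that calls never end would contradict them.

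Missed doses continue to be recorded under 6.4. The cost is a short protocol amendment and a few calls to poorly adherent participants, all within the seven already planned. The change concerns data collection only.

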## 7.3 LOST TO FOLLOW-UP

A participant will be considered lost to follow-up if he or she fails to return for seven consecutive scheduled telephone visits and is unable to be contacted by the study site staff.

The following actions must be taken if a participant fails to return a missed telephone contact for a required study visit:

- The site will attempt to contact the participant to reschedule the missed visit within the same business day as the originally scheduled appointment, counsel the participant on the importance of maintaining the assigned visit schedule, and ascertain if the participant wishes to and/or should continue in the study.
- Before a participant is deemed lost to follow-up, the investigator or designee will make every effort to regain contact with the participant (where possible, 3 telephone call attempts within the same business day). These contact attempts should be documented in the participant's medical record or study file.
- Should the participant continue to be unreachable, he or she will be considered to have withdrawn from the study with a primary reason of lost to follow-up.

# 8 STUDY ASSESSMENTS AND PROCEDURES

## 8.1 EFFICACY ASSESSMENTS

Patients presenting to MUHC emergency department for cold and flu-like symptoms during the study period will be assessed for eligibility by the admitting physician based on protocol inclusion and

exclusion criteria as previously detailed. Standard evaluation and collection of patient overall health status including past medical history, vital signs, physical exam, necessary imaging, and laboratory assessment will be completed as part of routine care associated with the emergency department visit. Patients enrolled into the study will be randomized and provided study drug the same day of their emergency department visit such that patients will not discharge from the emergency department until they have received their study drug and corresponding instructions for study participation. Testing results including COVID-19 status or positive influenza will be communicated via telephone contact to study patients as part of routine care follow-up and in accordance with MUHC emergency department procedures. Patients meeting exclusion criteria following results of study related testing information will be instructed to discontinue study intervention and follow-up with their primary care provider or other non-study related healthcare provider for appropriate management.

Upon receiving study drug and following discharge from the emergency department study subjects will begin self-administering study product as outlined in section 6.1.2 of this protocol the evening of the day of enrollment. Research staff from the MUHC emergency department will begin contacting patients the following day and daily thereafter for a total of seven consecutive days as described in section 1.3 of this protocol. The following data elements are to be collected each day via telephone visits for the efficacy endpoints:

Primary efficacy endpoints:

Symptom	Severity Score 0 – absent, 1- mild, 2- moderately sever, 3 – very severe
nasal drainage	
nasal congestion	
sneezing	
scratchy throat	
sore throat	
cough	
headache	
hoarseness	
muscle ache	
shivering or feverish	
tiredness	
difficulty in concentration	
Total Severity Score (max: 36 points)	

Recovery from cold and flu-like illness defined as daily total symptom severity score of 0 or 1	Yes or No
day 2	
day 3	
day 4	
day 5	
day 6	

day 7	
day 8	

Secondary efficacy endpoints:

Morbidity Event	Yes or No
missed days from work or school number of days	

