## 9.2 SAMPLE SIZE DETERMINATION

The target number of subjects to be enrolled during the study period occurring May 2022 – June 2023 is 100 (50 patients randomized to placebo and 50 to the supplementation group). This target is derived from a similarly conducted study evaluating zinc supplementation (without green tea extract) in a comparable adult population as identified with the current proposal. Based on an assumption that 60% of patients taking study drug and 30% in the placebo group would recover from cold and flu-like symptoms after five days of treatment a total of 84 patients would be sufficient to reach 80% power with a two tailed p value <0.05 to detect differences between groups. The power calculation was

$$N_1 = \left\{ z_{1-\alpha/2} * \sqrt{\bar{p} * \bar{q} * (1 + \frac{1}{k})} + z_{1-\beta} * \sqrt{p_1 * q_1 + (\frac{p_2 * q_2}{k})} \right\}^2 / \Delta^2$$

$$q_1 = 1 - p_1$$

$$q_2 = 1 - p_2$$

$$\bar{p} = \frac{p_1 + kp_2}{1 + K}$$

$$\bar{q} = 1 - \bar{p}$$

$$N_1 = \left\{ 1.96 * \sqrt{0.45 * 0.55 * (1 + \frac{1}{1})} + 0.84 * \sqrt{0.3 * 0.7 + (\frac{0.6 * 0.4}{1})} \right\}^2 / 0.3^2$$

$$N_1 = 42$$

$$N_2 = K * N_1 = 42$$

$p_1, p_2$  = proportion (incidence) of groups #1 and #2  
 $\Delta = |p_2 - p_1|$  = absolute difference between two proportions  
 $n_1$  = sample size for group #1  
 $n_2$  = sample size for group #2  
 $\alpha$  = probability of type I error (usually 0.05)  
 $\beta$  = probability of type II error (usually 0.2)  
 $z$  = critical Z value for a given  $\alpha$  or  $\beta$   
 $K$  = ratio of sample size for group #2 to group #1

performed using an online tool located at <https://clincalc.com/stats/samplesize.aspx> with the following calculations performed:

The anticipated dropout rate is 5% based on a large randomized control study evaluating safety of EGCG following 12 months of treatment using a similar daily dosage as the current proposal. No interim analysis is planned; power calculation is for primary endpoint only.

The primary outcome will be compared using the Chi-square test. Secondary outcomes will be assessed using the Chi-square test for categorical data and student's t-test for continuous data. An exploratory analysis comparing the primary outcome among COVID-19 only patients will also be conducted. All inferential testing will be based on intention-to-treat.

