#### 9.4.2 ANALYSIS OF THE PRIMARY EFFICACY ENDPOINT(S)

The primary endpoint will be determined from observing the proportion of patients (expressed as percentage) recovered from cold and flu-like symptoms (defined as scoring 0 or 1 daily total symptom severity score) following seven days of follow-up. Recovery from cold and flu-like symptoms will be categorically assessed as a single endpoint. The difference in recovery rates between study drug and placebo will be compared using Chi-squared test and be expressed with 95% confidence intervals. Analysis will be performed based on intention-to-treat. Missing data will be handled by last observation carried forward based on most recent self-reported total daily symptom severity score.

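### Participants who meet an exclusion criterion after randomisation can be withdrawn and replaced under 7.2, despite 7.1, leaving the primary analysis an early carried-forward score or none

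*Combined protocol and SAP*

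**What the plan says.** Sections 8.1 and 8.2 of the combined protocol and SAP have participants randomised and supplied with product before they leave the ED. COVID-19 and influenza results reach them later by telephone, as routine care. The protocol foresees the consequence: "Patients meeting exclusion criteria following results of study related testing information will be instructed to discontinue study intervention". These participants are also directed to a non-study provider for management. Neither section says whether the study calls go on.

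Section 5.2 defines the relevant exclusions by treatment. For influenza it is a positive test with oseltamivir or baloxavir planned. For COVID-19 it is current or planned treatment with a regulated drug.

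Two sections bear on follow-up:
- Section 7.1: "Discontinuation from study supplement or placebo does not mean discontinuation from the study", and the remaining procedures should be completed.
- Section 7.2 lists reasons for which the investigator may discontinue or withdraw someone from the study. One is: "If the participant meets an exclusion criterion (either newly developed or not previously recognized) that precludes further study participation". It adds that treated participants who are withdrawn may be replaced.

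On analysis, 9.3 includes all randomised participants, and 9.4.2 states: "Missing data will be handled by last observation carried forward based on most recent self-reported total daily symptom severity score". The recovery table in 8.1 runs from day 2 to day 8, and the baseline list in 9.4.5 has no symptom score.

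**The concern.** A group that the protocol expects to arise after randomisation falls under two rules with different results for data collection. Under 7.1 its outcomes are observed to Day 8. Under 7.2 they can stop at any point, at the investigator's discretion, and a new participant can take the place.

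An intention-to-treat set fixes who is counted. It does not supply the outcome. For a participant withdrawn after one or two calls, the carried-forward score comes from early in the illness. For one withdrawn before the first call, 9.4.2 gives no value at all. The plan also does not say whether a replaced participant stays in the all-randomised set. At stake are the accuracy of the recovery rate in each arm and whether the analysis described in 9.3 can be carried out in full.

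**Working it through.** **1. The passages side by side**

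| Step | Section | Result |
|---|---|---|
| Exclusion criterion found after randomisation | 8.1, 8.2 | Product stopped; calls not mentioned |
| Product stopped | 7.1 | Remains in study, procedures completed |
| Exclusion criterion newly recognised | 7.2 | May be withdrawn and replaced |
| Withdrawn from study | 6.3, 7.1 | Calls end; 6.3 calls only those not removed |
| Early withdrawal data | 8.1 | Four administrative items, no symptom score |
| Analysis | 9.3, 9.4.2 | All randomised; last score carried forward |

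Sections 7.1 and 7.2 can both apply to the same person, and nothing says which prevails.

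**2. The plan's own sample size.** Section 9.2: "Based on an assumption that 60% of patients taking study drug and 30% in the placebo group would recover"; "a total of 84 patients would be sufficient to reach 80% power with a two tailed p value <0.05". With the printed formula,

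n = {1.96·√(0.45·0.55·2) + 0.84·√(0.3·0.7 + 0.6·0.4)}² / 0.3² = (1.379 + 0.563)² / 0.09 = 41.92,

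which rounds up to 42 per arm, 84 in total. The plan's figure reproduces. The target is larger: "50 patients randomized to placebo and 50 to the supplementation group". At 50 per arm the exact power of the Pearson chi-square test is 87.6% (86.6% by normal approximation).

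**3. Effect on recovery rates.** Let r be the share withdrawn early, equal in both arms. This is an assumption; the documents give no figure. Let q be the recovery these participants would show if followed, taken as equal in both arms because they have stopped product. This is also an assumption, with range 30% to 60%.

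- Carried forward as not recovered: 0.6(1−r) against 0.3(1−r).
- Followed to Day 8: 0.6(1−r) + qr against 0.3(1−r) + qr.

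| r | Carried as not recovered | Followed, q = 30% to 60% | Understated by qr | Difference, both ways |
|---|---|---|---|---|
| 10% | 54% v 27% | 57–60% v 30–33% | 3–6 points | 27 points |
| 20% | 48% v 24% | 54–60% v 30–36% | 6–12 points | 24 points |

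Both arms' rates are too low by the same amount, and the difference between arms is unchanged.

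**4. Effect on power.** Exact Pearson chi-square, 50 per arm, two-sided 5%, no replacement:

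| r | Carried as not recovered | Followed, q = 30% to 60% |
|---|---|---|
| 5% | 84.2% | 84.0–84.1% |
| 10% | 80.3% | 79.8–80.0% |
| 15% | 76.0% | 75.1–75.3% |
| 20% | 71.5% | 69.9–70.2% |

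The loss against 87.6% comes from stopping product, not from losing the scores. Follow-up regains power only if brief exposure keeps some effect. For illustration, suppose affected participants recover at 45% on active and 30% on placebo, with r = 10%. The rates are then 0.6·0.9 + 0.45·0.1 = 58.5% against 30%, and power is 84.1%.

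**5. Replacement.** If replaced participants stay in the analysis and are carried as not recovered, there are 50/(1−r) per arm: 55.6 at r = 10% and 62.5 at r = 20%. Power by normal approximation is 83.6% and 80.6%. If they are removed from the set, the analysis is no longer of everyone randomised.

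**The case against.** The strongest reply is that the protocol already handles this. Section 8.1 stops only the product; sending the participant to another provider concerns care. Section 7.1 then keeps the participant in the study by default. Withdrawal under 7.2 is permissive, is limited to an exclusion that precludes further participation, and is decided blind to arm. That stands as a limit on how often data would be lost. It does not remove the conflict, because 7.2 describes this group and permits the opposite of 7.1 without saying when.

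Four stronger readings are tempting, and the documents do not support them.

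- A reader might infer that every participant with a positive test stops product. Section 5.2 ties the exclusion to treatment, and 9.4.9 keeps COVID-19 positives as an exploratory subgroup. The affected group is smaller than all virus-confirmed patients.
- A reader might take the fall in power as r rises as the price of ending the calls. Step 4 shows nearly the same fall with full follow-up if recovery is equal in both arms.
- A reader might infer bias between arms. Test results do not depend on allocation and the trial is double-blind, so losses should be about equal.
- A reader might infer that everyone withdrawn counts as not recovered. A last score of 0 or 1 would count as recovered.

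It is also fair to say that the lack of a rule for a participant with no score is a general gap in 9.4.2. It affects anyone never reached, whatever the reason.

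**Conclusion.** The point holds in limited form. The current text lets the outcomes of randomised participants be discarded by discretion, in a group the protocol itself anticipates. It then relies on an early carried-forward score, or on none, in an analysis meant to include everyone randomised. The consequence is misstated recovery rates in both arms and an incomplete intention-to-treat analysis.

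The size depends on the share affected, which the documents do not give. At an assumed 10% the understatement is 3 to 6 points per arm, and at 20% it is 6 to 12 points. This takes last scores to be above 1 and recovery, if followed, to be 30% to 60% in both arms. No between-arm bias is expected, and no power gain can be claimed for the fix unless brief exposure retains some effect. Severity is minor; the change is a cheap improvement.

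**What to change.** - In 8.1, 8.2 and 7.2, state that a participant who stops product because of a test result obtained after randomisation stays in the daily calls through Day 8 unless consent is withdrawn, and is analysed as randomised. This brings those sections into line with 7.1.
- In 7.2, remove meeting an exclusion criterion as a reason to end data collection.
- In 7.2 and 9.3, state that any replaced participant remains in the intention-to-treat set.

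The cost is a few sentences and at most seven calls per affected participant, all already in the schedule of activities. The clinical decision to stop product is not in question. These edits reduce the number of participants with no score. They do not supply a rule for those who still have none, which 9.4.2 needs in any case.
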